## 7.2 Summary of Treatment Visits

### 7.2.1 Screening

The Screening Visit must be performed within 28 days of Visit 1/baseline. Subject informed consent must be obtained prior to initiation of any study-specified procedures. A central reviewer and the sponsor will review eligibility criteria for all subjects.

A standard multi-lead video-EEG with HV and photic stimulation (PS) will be obtained over 30 minutes and will be followed by an additional 6-hour awake video-EEG (total, 6.5 hours). Subjects will undergo HV for 5 minutes (HV period 1). If no absence seizure occurs, the subject will rest for 5 minutes and then undergo HV for an additional 5 minutes (HV period 2). Further details, including procedures for HV and PS will be elaborated in the EEG Charter.

Subjects will begin documenting absence seizure-free days in a daily diary and will continue to do so for the duration of the study. See [Table 3](#) for a detailed list of assessments to be performed.

### 7.2.2 Visit 1 (Day 0 - Baseline)

Subjects will return to the clinic within 28 days of screening. Following confirmation of continued eligibility by the central reviewer and sponsor, subjects will receive the first dose of study drug (2 mg or placebo) with food and undergo assessments as detailed in Table 3. Subjects will be followed for adverse events, orthostatic vital signs, and ECG for at least 2 hours prior to discharge. The investigator or qualified designee will make the determination of whether it is safe to release the subject from the clinic. Subjects will be instructed to take the second daily dose of study drug no sooner than 10 hours and no later than 14 hours (every 12 hours  $\pm$  2 hours) from the time of their first dose.

### 7.2.3 At Home Dose Titration (Days 1-26)

Subjects will continue twice daily dosing for 4 weeks according to the dose titration schedule detailed in [Section 4.3](#).

### 7.2.4 Telephone Safety Check (Day 2)

Prior to initiating the 4 mg BID dose, study staff will contact subjects by telephone to query the subject on their health status, including the occurrence of any AEs. Subjects who are experiencing any AEs may be asked to return to the clinic for an unscheduled visit. Subjects who are experiencing nervous or psychiatric system-related AEs should return to the clinic for an unscheduled visit.

### 7.2.5 Telephone Safety Check (Day 8)

Prior to initiating the 6 mg BID dose, the study staff will contact the subjects by telephone to query them about their health status, including the occurrence of any AEs. Subjects who are experiencing any AEs may be asked to return for an unscheduled visit. Subjects who are

experiencing nervous or psychiatric system-related AEs should return to the clinic for an unscheduled visit. The telephone call may take place on Day 6, 7, or 8.

#### **7.2.6      Telephone Safety Check (Day 14)**

Prior to initiating the 8 mg BID dose, study staff will contact subjects by telephone to query the subject on their health status, including the occurrence of any AEs. Subjects who are experiencing any AEs may be asked to return for an unscheduled visit. Subjects who are experiencing any nervous or psychiatric system-related AEs should return to the clinic for an unscheduled visit. This call may take place on Day 12, 13, or 14.

#### **7.2.7      Telephone Safety Check (Day 20)**

Prior to initiating the 10 mg BID dose, the study staff will contact the subjects by telephone to query them about their health status, including the occurrence of any AEs. Subjects who are experiencing any AEs may be asked to return for an unscheduled visit. Subjects who are experiencing any nervous or psychiatric system-related AEs should return to the clinic for an unscheduled visit. The telephone call may take place on Day 18, 19, or 20.

#### **7.2.8      End of Study Visit (Day 26)**

Subjects will return to the clinic for the final visit assessments detailed in [Table 3](#). This visit may take place on Day 25, 26, or 27 as needed for scheduling. Subjects will be instructed to take their dose of study drug before reporting to the clinic.

A standard multi-lead video-EEG with HV and photic stimulation (PS) will be obtained over 30 minutes and will be followed by an additional 6-hour awake video-EEG (total, 6.5 hours). During this time, safety assessments, as shown in Table 3, will be conducted, and 2 PK blood samples, separated by >2 hours, will be obtained. Subjects will undergo HV for 5 minutes (HV period 1). If no absence seizure occurs, after a 5-minute rest, subjects will undergo HV for an additional 5 minutes (HV period 2). Further details, including procedures for HV and PS will be elaborated in the EEG Charter. Adverse events that are unresolved at the visit will continue to be followed by study staff as detailed in [Section 10.2.3](#).

#### **7.2.9      Telephone Safety Check (Day 33)**

One week after the End of Study Visit, the study staff will contact the subjects by telephone to query them about their health status, including the occurrence of any AEs. Subjects who are experiencing any AEs may be asked to return for an unscheduled visit. Subjects who are experiencing any nervous or psychiatric system-related AEs should return to the clinic for an unscheduled visit. Any AEs that remain unresolved at this visit will be noted as ongoing. This telephone call may take place on Day 32, 33, or 34.

#### **7.2.10     Follow-up Phone Call**

Study staff will contact each subject by phone 30 days after the last dose of study drug for evaluation of the occurrence of any SAEs.

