- 8) Subjects with reproductive capability, including all males and WOCBP, must agree to practice continuous abstinence or adequate contraception methods (appropriate double barrier method or oral, patch, implant, or injectable contraception) from as soon as feasible during screening period until at least 30 days after the last dose (i.e., intermittent abstinence based on "rhythm," temperature monitoring, or other means of timing is not acceptable). WOCBP include any woman who has experienced menarche and who has not undergone successful surgical sterilization (hysterectomy, bilateral tubal ligation, and/or bilateral oophorectomy) or is not postmenopausal. Postmenopausal is defined as amenorrhea for  $\geq 12$  consecutive months without another cause, and a documented serum follicle stimulating hormone (FSH) level  $\geq 35$  mIU/mL.
- 9) Male subjects with a partner of childbearing potential must be surgically sterilized or be willing to use condoms with spermicide from as soon as feasible during screening period until at least 30 days after the last dose.
- 10) Able and willing to comply with scheduled visits, treatment plan, laboratory tests, and other study procedures.
- 11) Approval by the sponsor medical personnel or delegate as to final eligibility for the study.

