#### Treatment Period

The treatment period is the period during which a subject receives study drug (i.e., first dose through Day 26).

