## 10.3 Serious and Other Significant Adverse Events

### 10.3.1 Definition of a Serious Adverse Event

A serious adverse event is any adverse event that

- **Results in death.** Death is not an event per se but rather an outcome. Note that any AE resulting in a fatal outcome must be fully documented and reported, including deaths that occur within 30 days after treatment ends and irrespective of the causal relationship to the study drug.
- **Is life threatening.** Life threatening refers to an AE in which the subject was at immediate risk of death at the time of the event. It does not refer to an event, which may have caused death, if it was more severe.
- **Requires inpatient hospitalization or prolongation of existing hospitalization.** Hospitalization means that the subject was admitted to hospital or that existing hospitalization was extended as a result of an AE. Hospitalization describes a period of at least 24 hours. Over-night stays for observation, stays at the emergency room or treatment on an outpatient basis do not constitute a hospitalization. However, medical judgment must always be exercised and, when in doubt, the case should be considered serious (i.e., if the case fulfills the criterion for a medically important event). Hospitalization for administrative or social purposes does not constitute an SAE. Hospital admissions and/or surgical operations planned before study inclusion are not considered AEs if the illness or disease existed before the subject was enrolled in the study, provided that the condition did not deteriorate during the study.
- **Results in persistent or significant disability/incapacity.** Disability/incapacity means a substantial disruption of a person's ability to conduct normal life functions. If in doubt, the decision should be left to medical judgment by the investigator.
- **Is a congenital anomaly/birth defect.** Any congenital anomaly or birth defect observed in any offspring of the subject that was conceived during treatment with the study drug.

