#### **10.3.4      Reporting and Follow-up of Pregnancy**

When an investigator becomes aware of the pregnancy of a female subject (or female partner of a male subject), the investigator must withdraw the subject from the study treatment and follow the pregnancy until termination or until the child is 1 month old. The pregnancy will be reported immediately by telephone and by faxing a completed Pregnancy Report to the sponsor within 24 hours of knowledge of the event. The pregnancy will not be processed as an SAE; however, the investigator should notify the sponsor or the sponsor's agent of the outcome of the pregnancy by submitting a follow-up Pregnancy Report. Additionally, if the outcome of the pregnancy meets the criteria for immediate classification of an SAE (e.g., spontaneous or therapeutic abortion, stillbirth, neonatal death, congenital anomaly), the investigator will report the event by phone and by faxing a completed SAE Report Form to the sponsor within 24 hours of knowledge of the event.

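### After Day 26 no scheduled test or specified question covers pregnancy, although contraception is required for 30 more days, and male subjects' partners are never covered

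*Protocol*

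**What the plan says.** **Contraception period.** Protocol Section 6.2, criterion 8, applies to men and to women of childbearing potential "from as soon as feasible during screening period until at least 30 days after the last dose". Criterion 9 sets the same end point for men with a partner of childbearing potential.

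**Treatment period.** Section 10.2.1 defines it as "first dose through Day 26".

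**Tests.** Table 3 marks a urine pregnancy test at Screening and on Day 26 only. Section 10.1.6 limits testing to women of childbearing potential.

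**Contacts after Day 26.** On Day 33 (Section 7.2.9) staff are to "query them about their health status, including the occurrence of any AEs". The last contact is in Section 7.2.10: "Study staff will contact each subject by phone 30 days after the last dose of study drug for evaluation of the occurrence of any SAEs". Table 3 footnote 19 and Sections 10.1.1, 10.2.2 and 10.2.3 likewise limit this call to SAEs.

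**Pregnancy reporting.** Section 10.3.4 starts once the investigator learns of a pregnancy in a subject or a male subject's partner. It requires a report within 24 hours and follow-up to termination or until the child is 1 month old. It adds: "The pregnancy will not be processed as an SAE". Outcomes such as abortion, stillbirth, neonatal death or congenital anomaly are to be reported as SAEs. Section 10.3.1 lists among SAEs: "Any congenital anomaly or birth defect observed in any offspring of the subject that was conceived during treatment with the study drug".

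**The concern.** The protocol treats conception as a risk to be avoided for 30 days beyond the last dose, and it wants every pregnancy reported and followed. The schedule, however, contains no step that would bring a pregnancy to light in those 30 days. The final call, run as written, would not elicit an ongoing, uncomplicated pregnancy.

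The offspring SAE category depends on that step. A live-born anomaly after conception on treatment cannot be seen by the time of the final call, and routine SAE reporting closes 30 days after the last dose (Section 10.3.2). That outcome can be captured only if the pregnancy is identified first and then followed under Section 10.3.4.

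Safety is the primary objective and only up to about 15 subjects are planned, so each exposed pregnancy that goes unrecorded is a real loss of information.

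**Working it through.** The plan gives no figure for this point, so the check is a count of days set against the scheduled contacts.

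**Inputs from the documents**
- Dosing: Day 1 to Day 26.
- End of the contraception period: Day 26 + 30 = Day 56.
- Last pregnancy test: Day 26 (the visit may fall on Day 25 to 27).
- Final call: 30 days after the last dose, so Day 56. Table 3 shows Day 57 ± 2 days, which includes it.
- Terminal half-life after single doses (Appendix D): 9.7 to 13.2 hours in young men, 18.8 to 22.6 hours in elderly men.

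**Assumption not in the documents:** a urine test turns positive *L* days after conception, with *L* between 10 and 14.

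**Step 1. Contacts compared with what each could reveal**

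| Contact | Content | Ongoing pregnancy in subject | Pregnancy in partner |
|---|---|---|---|
| Day 26 visit | Urine test in women of childbearing potential | Yes, if conceived early enough | No |
| Day 33 call | General health and adverse events | Only if volunteered | Only if volunteered |
| 30-day call | SAEs | Not asked | Not asked |

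The calls before Day 26 (Days 2, 8, 14 and 20) also cover only health status and adverse events, so partners have no specified check at any time.

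**Step 2. Days after the last test, with no lag assumed.** Days 27 to 56 are 30 of the 56 days from Day 1: 30/56 = 54%.

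**Step 3. Dosing days too recent for the Day 26 test.** The share is *L*/26:
- *L* = 10: 10/26 = 38%
- *L* = 14: 14/26 = 54%

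**Step 4. A narrower window, with drug still present.** Five half-lives is a convention, not a figure in the documents. It gives 5 × 13.2/24 = 2.8 days to 5 × 22.6/24 = 4.7 days after the last dose, or about Day 29 to Day 31. The share beyond the reach of the Day 26 test is (*E* − 26 + *L*)/*E*, where *E* is the last day of the window:
- *E* = 29: 13/29 = 45% (*L* = 10), 17/29 = 59% (*L* = 14)
- *E* = 31: 15/31 = 48% (*L* = 10), 19/31 = 61% (*L* = 14)

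If a full 28-day screening period is added to the denominator, the range is 13/57 = 23% to 19/59 = 32%.

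**Step 5. Schedule under which subjects enrolled.** SAP Section 1.1 says no subject enrolled under amendments 4 and 5, and it presents the amendment 3 schedule. That schedule also has tests only at Screening and Day 26 and a 30-day call for SAEs, with a last dose on Day 27. Days 27 to 57 then follow the last test: 31/57 = 54%. The gap is the same.

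**The case against.** The strongest reply is that the protocol already provides for pregnancy. Section 10.3.4 covers subjects and partners, sets a 24-hour deadline, and states no cut-off date for becoming aware. Day 33 is an open health query at which a known pregnancy could be mentioned. Adverse outcomes such as abortion or stillbirth are SAEs and fall within the final call if they have occurred by then. Consent pages were removed from the material, and call scripts and CRFs are not part of it, so subjects may have been told to report a pregnancy. All of this stands. It shows that passive routes exist, but none of it is a scheduled question about pregnancy.

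Three stronger readings are tempting, and the documents do not support them.

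- **That most exposed conceptions escape any check.** A reader might add a 14-day lag to the 30 days, get 44/56 = 79%, and treat that as a share of exposed conceptions. The denominator is the contraception period, not exposure. On the protocol's half-lives the share is 45% to 61%, so whether it exceeds half depends on an assumed lag. It falls to 23% to 32% if screening conceptions count. It also measures only what the Day 26 test cannot detect, and gives the later calls no yield.
- **That safety follow-up ends before the risk period.** The final call and the required contraception period both end 30 days after the last dose, and a reported pregnancy is followed well beyond that. The offspring SAE covers only conception during treatment.
- **That the toxicology shows a fetal hazard at the study dose.** Appendix C reports reduced rat fetal weight at 100 mg/kg/day and above, but with maternal toxicity at 300 and below. The rabbit study found no developmental toxicity at 300 and below. Neither study has exposure data. The point does not rest on this.

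**Conclusion.** The point holds as a gap in data collection. No scheduled test or specified question addresses pregnancy in the 30 days after the last dose in which contraception is still required, which is 30 of 56 days (54%) with no assumption about test lag. The Day 26 test also misses conceptions late in dosing: 38% to 54% of dosing days, resting on an assumed lag of 10 to 14 days. Partners of male subjects have no scheduled check at any time, and that needs no assumption.

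These are shares of calendar days. Reading them as shares of conceptions would further assume an even daily chance of conception. The documents give no conception rate, and with mandatory contraception and about 15 subjects of both sexes the expected number is likely to be small. The case for acting is that an SAE-only call, run as written, would not pick up an ongoing pregnancy, and that the remedy is nearly free.

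**What to change.** Reconcile Section 6.2 (criteria 8 and 9), Sections 7.2.9 and 7.2.10, Table 3 footnote 19 and Section 10.3.4, so that the Day 33 call and the 30-day post-dose call also record any pregnancy in the subject or a male subject's partner, for reporting under Section 10.3.4. Sections 10.1.1, 10.2.2 and 10.2.3, which repeat the SAE-only description of the final call, need the same wording. No visit, test, dose or treatment rule changes.

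The cost is one question on two existing calls and one CRF field. The gain is partial. At a 14-day lag a question on Day 56 could reach conceptions up to about Day 42 (56 − 14), which includes all dosing days and the five-half-life tail to Day 31. Conceptions in about the last two weeks of the contraception period would still be missed, and any answer depends on what the subject knows by then.

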## **7.3 Concomitant Medications and Other Restrictions**

### **7.3.1 Concomitant Medications**

The use of prescription or nonprescription drugs or other products (e.g., grapefruit juice) known to be strong inhibitors or inducers of CYP3A4 must be discontinued 2 weeks prior to Day 1 of dosing and withheld throughout the study. See [Appendix B](#) for a complete list of restricted inhibitors and inducers.

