### **6.2 Inclusion Criteria**

Subjects may be included in the study only if they meet all of the following criteria. Subjects may undergo rescreening following consultation with and approval of the Study Safety Representative.

- 1) Signed informed consent form (ICF) indicating that the subject has been informed of the procedures to be followed, the experimental nature of the therapy, alternatives, potential benefits, side effects, risks, and discomforts.
- 2) Men or nonpregnant, non-breastfeeding women 16 to 55 years of age who are able to read and understand the written and spoken local language.
- 3) Clinical diagnosis of IGE (including, but not limited to, CAE, JAE, juvenile myoclonic epilepsy, or Jeavons syndrome) with absence seizures consistent with the International League against Epilepsy Revised Classification of Seizures (2017).
- 4) Absence seizures, by history on average once per hour, persisting despite standard of care (SOC) treatment, defined as treatment with at least 2 AEDs appropriate for the patient's epilepsy syndrome. SOC failure, per investigator discretion, will be defined as insufficient clinical response or intolerable side effects, which precludes use of the appropriate AED.

- 5) Observation of at least 1 provoked absence seizure during at least 1 of the hyperventilation (HV) periods and at least 3 absence seizures during the 6.5-hour video-EEG. Absence seizures are defined on EEG as typical generalized 3-Hz spike and wave lasting  $\geq 3$  seconds during wakefulness. Hyperventilation should be carried out in the following manner: 5 minutes of HV (HV period 1), followed by 5 minutes of relaxation, followed by a second 5 minutes of HV (HV period 2). Subjects who have an induced seizure during HV period 1 do not need to undergo HV period 2. At least 75% of the background should be normal.
- 6) On stable doses of one or more antiepileptic medication(s) for at least 30 days. If a subject is not on medication, adequate documentation justifying lack of therapy may be acceptable for the subject after sponsor review. Ketogenic, modified Atkins diet (MAD), or low glycemic diet with stable carbohydrate ratio for at least 30 days before screening is an acceptable antiepileptic therapy. Vagal nerve stimulation at stable settings (for at least 30 days before screening), without use of the magnet, is also acceptable.
- 7) Body weight  $\geq 45$  kg at screening.

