### **6.3 Exclusion Criteria**

Subjects will be excluded from the study if any of the following conditions apply. Subjects may undergo rescreening following consultation with and approval of the Study Safety Representative.

- 1) History of surgical intervention for treatment of epilepsy.
- 2) Additional seizure (clinical and electrographic) types, including, but not limited to, epileptic spasms, generalized tonic seizures, atonic seizures, or focal seizures. Subjects with GTCS or myoclonic seizures are eligible for the study.
- 3) Inadequately treated psychotic or mood disorder (e.g., schizophrenia, major depression, bipolar disorder).
- 4) Presence of severe intellectual disability, severe autism spectrum disorder, or severe developmental disorder such that the subject cannot sign the ICF or cannot cooperate with the study procedures.

- 5) Presence of positive urine drug screen for drugs of abuse, except if this is explained by use of an allowed prescription medicine.
- 6) Regular use of more than 2 standard drinks of alcohol per day (28 grams of pure alcohol).
- 7) Hypersensitivity/allergic reaction to other T-type calcium agents, such as (but not limited to) ethosuximide and zonisamide.
- 8) Use of strong CYP3A4 inhibitors, including prescription or nonprescription drugs or other products (e.g., grapefruit juice), which cannot be discontinued at least 2 weeks prior to Day 1 of dosing and throughout the study ([Appendix B](#)).
- 9) Concurrent illnesses that would be a contraindication to trial participation, including, but not limited to:
  - a) Severe arterial thromboembolic events (myocardial infarction, unstable angina pectoris, stroke) less than 6 months before screening.
  - b) New York Heart Association (NYHA) Class III or IV congestive heart failure, ventricular arrhythmias or uncontrolled blood pressure.
  - c) Clinically significant ECG abnormality per the investigator assessment or any of the following:
    - i. QTcF  $\geq$ 450 msec (males) or  $\geq$ 470 msec (females).
    - ii. PR interval  $\geq$ 250 msec.
    - iii. Atrioventricular block of second degree or higher, including Mobitz I.
    - iv. Persistent sinus bradycardia of  $\leq$ 50 beats per minute; persistent means the bradycardia is present on the first ECG and on one repeat ECG performed on another day.

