## Appendix B – Cytochrome P450 Drug Interaction Table

### PROHIBITED CYP3A4 INHIBITORS\*

HIV antivirals (delavirdine, indinavir, nelfinavir, ritonavir)  
amiodarone  
cimetidine  
clarithromycin  
diltiazem  
erythromycin  
fluvoxamine  
grapefruit juice  
itraconazole  
ketoconazole  
nefazodone  
suboxone  
troleanomycin  
verapamil

Prohibited moderate and strong inhibitors of CYP3A4 and CYP2C9 include the lists above, but are not limited to the medications and agents listed

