### PROHIBITED CYP3A4 INDUCERS\*

carbamazepine  
efavirenz  
nevirapine  
phenobarbital  
phenytoin  
pioglitazone  
primidone  
rifabutin  
rifampin  
St. John's Wort  
troglitazone

Prohibited moderate and strong inducers of CYP3A4 and CYP2C9 include the lists above, but are not limited to the medications and agents listed

*From: Flockhart DA. Drug Interactions: Cytochrome P450 Drug Interaction Table. Indiana University School of Medicine (2007). "/clinpharm/ddis/clinical-table/" Accessed [6 Dec 2016].*

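### Exclusion 8, Section 7.3.1 and Appendix B set three different CYP scopes, and no rule says to exclude a subject on a listed inducing antiepileptic rather than stop the drug

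*Protocol*

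**What the plan says.** **Exclusion 8** (synopsis and Section 6.3) excludes "Use of strong CYP3A4 inhibitors, including prescription or nonprescription drugs or other products (e.g., grapefruit juice), which cannot be discontinued" at least two weeks before Day 1 and for the duration of the study. It ends with a reference to Appendix B.

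**Section 7.3.1** covers products known to be "strong inhibitors or inducers of CYP3A4 must be discontinued 2 weeks prior to Day 1 of dosing and withheld throughout the study". It sends the reader to Appendix B "for a complete list of restricted inhibitors and inducers".

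**Appendix B** says of inhibitors: "Prohibited moderate and strong inhibitors of CYP3A4 and CYP2C9 include the lists above, but are not limited to the medications and agents listed". It says of inducers: "Prohibited moderate and strong inducers of CYP3A4 and CYP2C9 include the lists above, but are not limited to the medications and agents listed". The CYP3A4 inducers it names include carbamazepine, phenobarbital, phenytoin and primidone.

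**Inclusion 6** requires subjects to be "On stable doses of one or more antiepileptic medication(s) for at least 30 days". It gives no date from which the 30 days are counted for drugs. For diet it does: "low glycemic diet with stable carbohydrate ratio for at least 30 days before screening is an acceptable antiepileptic therapy". It also allows for untreated subjects: "If a subject is not on medication, adequate documentation justifying lack of therapy may be acceptable for the subject after sponsor review".

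**Review.** Section 5.2 bars enrolment and dosing until the central reviewer and review process have found the subject eligible. Section 7.2.2 has continued eligibility confirmed before the first dose. Inclusion 11 makes sponsor medical approval an entry criterion.

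**The concern.** The population has absence seizures that persist despite at least two antiepileptics (inclusion 4), and subjects with generalized tonic-clonic seizures are eligible (exclusion 2). Nearly everyone screened will be on background therapy. If a concomitant-medication rule reaches a background antiepileptic and the eligibility criteria do not, stopping that drug can become the way into a 26-day open-label study.

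Two things are at stake. The first is safety: a patient with uncontrolled seizures could lose a background drug for study entry, with no taper, substitution or exemption described. The second is attribution. There is no control arm, and increased seizure frequency, new seizure types and status epilepticus are adverse events of special interest within the primary endpoint (Protocol 3.3.1, SAP 5.3.1). Worsening after the first dose in such a subject could come from the withdrawal or from CX-8998.

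**Working it through.** The check is mainly a comparison of texts.

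**Step 1. Scope of each text.**

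| Text | Enzymes | Strength | Direction | Status of the list |
|---|---|---|---|---|
| Exclusion 8 | CYP3A4 | strong | inhibitors | cites Appendix B |
| Section 7.3.1 | CYP3A4 | strong | inhibitors and inducers | calls Appendix B complete |
| Appendix B | CYP3A4 and CYP2C9 | moderate and strong | inhibitors and inducers | says it is not exhaustive |

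The three rows differ, and the last column contradicts itself: the list cannot be both complete and open-ended.

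**Step 2. A subject stable on phenytoin.** Section 1.2.2 itself names phenytoin as an antiepileptic, so the argument stands on that drug alone.
- Inclusion 6: met on its wording, since no antiepileptic is excepted.
- Exclusion 8: not triggered on its wording, since phenytoin is listed as an inducer.
- Section 7.3.1: its duty to stop covers strong agents, and its list is Appendix B, which includes phenytoin. On one natural reading the drug has to stop two weeks before Day 1.
- Appendix B: phenytoin is prohibited, but nothing says whether to exclude the subject or withdraw the drug.

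**Step 3. Calendar.** Screening runs from Day -28 to Day -1 (Table 3). The SAP Study Day formula has no Day 0, so Day -28 is 28 days and Day -14 is 14 days before Day 1. A stop made after consent in the same screening period that meets the two-week rule falls between Day -28 and Day -14.
- Days off drug at Day 1: 14 to 28.
- Day 26 is 26 - 1 = 25 days after Day 1.
- Days off drug at Day 26: 14 + 25 = 39 to 28 + 25 = 53.

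These are nominal, because the Day 26 visit may fall on Day 25 to 27. They show only that treatment would follow soon after the stop. They do not measure harm.

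**Step 4. Does inclusion 6 block it?** Not reliably. Counted back from screening, the 30 days can be met before the stop. Counted back from Day 1, 14 to 28 days falls short of 30 for the stopped drug. Even then the criterion asks for only one or more stable antiepileptics, and it can admit justified unmedicated subjects.

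**The case against.** The strongest case on the other side has four parts.

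- **Exclusion 8 also cites Appendix B**, so the link to the inducer list may already exist on the eligibility side. This has some weight, but the criterion's operative word is inhibitors. Even if the whole appendix is imported, the criterion removes only subjects whose drug cannot be discontinued. A subject able to stop phenytoin is still admitted by stopping it.
- **The duty to stop is limited to strong agents.** No text grades phenytoin, Appendix B mixes moderate with strong, and a prohibited list can be read as an instruction not to enrol. This stands. A reader might infer that the protocol plainly orders withdrawal of phenytoin; the documents support that only as one reading.
- **The review is mandatory.** Eligibility is checked at screening and again on Day 1, nobody is dosed before clearance, inclusion 11 requires sponsor approval, and inclusion 10 requires ability to follow the treatment plan. A subject left unmedicated would also need documentation and sponsor review under inclusion 6. These safeguards are real and narrow the problem. They depend on judgement, however, and the reviewers have no written rule preferring exclusion to withdrawal.
- **The attribution problem is partly contained.** Adverse events are recorded from consent, and worsening that begins before dosing is treatment-emergent only if it intensifies on treatment. This also stands, although the diary records only whether any absence seizure occurred on a given day.

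**Conclusion.** The mismatch between the three texts is certain. That it can lead a site to stop a background antiepileptic for study entry is a reasonable reading, with no written rule against it. That is enough to justify a wording correction.

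The size is unknown. The documents do not say how many eligible subjects would take a listed inducer, and none of the absence treatments named in Section 1.1.2 is named in Appendix B, so the number may be small. The attribution concern applies only to a subject who actually stops a drug this way.

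A reader might infer that trial subjects were withdrawn from antiepileptics or that the reported safety results are confounded. The documents do not support that. SAP Section 1.1 states that nobody enrolled under amendments 4 and 5. The protocol text supplied, with video-EEG and no Day 27 dose, appears to match those amendments, and the amendment 3 wording is not available. No effect on enrolled subjects is claimed.

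**What to change.** 1. Extend exclusion 8, in the synopsis and Section 6.3, to the inducers in Appendix B.
2. State there and in Section 7.3.1 that subjects taking an inducing antiepileptic prohibited by Appendix B are excluded, and that no background antiepileptic may be withdrawn in order to qualify.
3. Make the enzyme and strength wording of exclusion 8 and Section 7.3.1 match Appendix B, and delete the word complete from Section 7.3.1.

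Appendix B is the natural reference because both other texts already point to it. The pharmacokinetic rationale is redacted, so whether its wider scope is pharmacologically necessary cannot be judged here.

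The cost is a few candidates who become ineligible, and a protocol amendment. No new assessment and no SAP change is needed. Giving the 30 days in inclusion 6 a start date for drugs would be tidy, but it is optional and not required for this correction.
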